^b All research assessments will be collected up to 7 days ahead of any IMP administration at these visits and prior to administration of any further IMP. New local prescriptions will be issued by the GP following instruction from the site teams at weeks 12 and week 24, or by sites for their pharmacy at 12 weeks and at 24 weeks for the patient to collect in the TAU arm.

^c All research assessments will be collected up to 7 days ahead of any IMP administration at these visits and the CRF updated at the visit.

^d Confirmed in writing in the clinical notes at each study visit.

^e Pregnancy test required at 36 weeks for all participants of childbearing potential or 7 days after this point if participants are still on TAU week 36^e

fMigraine history and MIDAS only repeated if positive at any of the previous visits. If reporting a new headache then ID-Migraine, migraine history and MIDAS are completed at that visit and the migraine history and MIDAS are repeated at subsequent visits.

§ Phone call to collect AE data in 7 days since week 36 visit. Only required if participant still receiving TAU IMP at week 36 or stopped IMP after week 35.

^h Qualitative interview will ideally take place during screening but may be up to 4 weeks after consent to the interview. This may be after the start of the IMP in some cases.

TAU prescription may be issued at any point during screening or at Day 0 as appropriate. Day 0 is the first dose of IMP.

Review of medication only at week 36

IMPORTANT: If participants who discontinue trial treatment plan to begin a new therapy for TMD (NHS or private) within the remainder of the trial monitoring period, they should be asked if they will complete the next set of research assessments prior to beginning a new treatment in routine clinical care and then go back on schedule to the next scheduled set of research assessments following this.

Key
AE & SAE - Adverse Event & Serious Adverse Event
BPSQI - Brief Pittsburgh Sleep Quality Index
CN V & VII - 5th Cranial Nerve and 7th Cranial Nerve
CPI (within GCPS) - Characteristic Pain Intensity (Graded Chronic
Pain Scale)
EQ-5D-5L - See section 7.4.6.4
FaCE - Facial Clinimetric Evaluation
GIC - Global impression of change

HUQ – Health Utilisation Questionnaire
MIDAS – Migraine Disability Assessment Test
LAEP - Liverpool adverse events profile
OHIP-TMDs - Oral Health Impact profile for TMD
PHQ-4 - Patient Health Questionnaire-4
PMH – Past Medical History

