100 units of Botox should be reconstituted with 2mls of 0.9% normal saline once the participant attends and confirms is going ahead with treatment. The vial's diaphragm should be wiped prior to reconstitution with a cleaning wipe. Brand of cleaning wipe will be determined by local aseptic non touch technique policy. Dosages per injection site are then:

- Masseter 10 units (0.2mls) per injection site = total 30 units per muscle
- Temporalis 5 units (0.1mls) per injection site = total 15 units per muscle
- Total dose per patient = 90 units. Maximum ceiling dose 100 units.

2mls of 2% Lidocaine will be used in same sites and volumes as for Botox. Volumes of Lidocaine per injection site are then:

- Masseter 0.2mls (4mg) per injection site = total 0.6ml per muscle
- Temporalis 0.1mls (2mg) per injection site = total 0.3ml per muscle
- Total dose per patient = 36mg. Maximum ceiling dose 40mg.

The cycles of injections provided will follow the schedule of events in section 7.4.10: day 0; week 12 +/- 7 days; week 24 +/- 7 days.

Doses selected for the injectable IMPs are based on the best quality evidence currently available for BTX and local anaesthetic injection therapy in M-TMD balancing risk of adverse effects against effectiveness (Al-Moraissi et al., 2020; Chan et al., 2016; De la Torre Canales et al., 2020; Machado et al., 2018; Nouged et al., 2019). The doses chosen provide the maximum chance of effectiveness and lowest chance of adverse effects, with the ceiling doses positioned well within the safety margin for the drug (\leq 25% of the total possible dose in one administration) and at the lowest end of the range of doses given to these muscles (Thambar et al., 2020). The BTX dosing scheduling is contemporary with current practice in the UK (Anwar et al., 2022) and consistent with the NICE recommendations for injectable (intramuscular) treatment of another trigeminally mediated pain (chronic migraine) which completes after the third cycle if no therapeutic effect is felt by the patient (Bendtsen et al., 2018; NICE, 2012). The Lidocaine dosing schedule is within the parameters within the published literature at the conservative end of repeated injections and mirrors the BTX scheduling given Lidocaine is an active comparator within the trial (Al-Moraissi et al., 2020; De la Torre Canales et al., 2020; Nouged et al., 2019).

Please note participants can elect to stop receiving any of the IMPs and can continue within the trial (details in section 7.6).

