9.2. Recording and Reporting AEs and SAEs

All AEs occurring from point of consent to end of trial participation must be recorded in the AE eCRF page as well as the participant's clinical notes.

For all AEs the following will be recorded: severity, seriousness, causality, and any concomitant medication used.

All SAEs occurring from point of consent to end of trial participation must be reported to NCTU on an SAE form and also recorded in the AE eCRF page and recorded as serious.

All SARs occurring from the 1st dose of IMP to the time periods specified in table 2 must be reported to NCTU on an SAE form and also recorded in the AE eCRF page.

Table 2 - Half-lives of IMPs and time period from last dose to end of SAR monitoring

Medication	Half life /hrs	Cleared (5 half lives) /hrs	Source	Time period from last trial dose (including any tapering dose) for end of SAR monitoring/days*
Oral amitriptyline	25	155	https://www.medicines.org.uk/emc/product/14334/smpc	7
Oral gabapentin	7	35	https://www.medicines.org.uk/emc/ product/158/smpc	7
IM Lidocaine 2%	1.68	8.4	https://pubmed.ncbi.nlm.nih.gov/74 39378/	7
IM Botox	10	50	https://www.ema.europa.eu/en/doc uments/referral/botox-article-29- referral-annex-i-ii-iii_en.pdf	7

^{*}Rounded up to nearest week. If pregnancy falls outside of this time period, it would not need to be reported for the trial or monitored for adverse effects

Following this defined active monitoring period for SARs, investigators are still required to report any SARs or SUSARs they become aware of.

All SAEs/SARs must be reported to NCTU on an SAE Form via secure email to [contact] as soon as possible and within 24 hours of research staff becoming aware of the event.

Preliminary reporting to NCTU via email or telephone is acceptable in order to meet the 24-hour reporting timeline, where circumstances do not allow for immediate completion of the SAE form. However, the SAE form should be completed and submitted as soon as possible after the initial notification in order to comply with reporting timelines.

For each SAE the following information will be collected:

- Full details in medical terms and case description
- Event duration (start and end dates, if applicable)
- Action taken

- Outcome
- Seriousness criteria
- Causality in the opinion of the investigator

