9.8. Pregnancy Reporting

In the event of a trial participant or the partner of a trial participant becoming pregnant on the trial, the site must notify NCTU, the Chief Investigator and the sponsor representative within 24 hours of becoming aware of the pregnancy. This is by completion of a pregnancy reporting form which should be sent to [contact].

Site must approach the trial participant or the partner of a trial participant to obtain consent to follow the pregnancy to completion. The outcome of the pregnancy will then be obtained when available.

Pregnancy in itself is not an SAE. In the event that a congenital anomaly or birth defect does occur, this must be reported as an SAE.

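### The Table 2 footnote and section 9.8 of the protocol give conflicting instructions on reporting a pregnancy that arises more than 7 days after the last trial dose but while the participant is still on the trial

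*Protocol*

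**What the plan says.** Section 9.2, Table 2, lists the four trial drugs with half-life, time to clearance at five half-lives, and a column headed "Time period from last trial dose (including any tapering dose) for end of SAR monitoring/days". The entry is 7 days for every drug. The footnote explains the figure ("Rounded up to nearest week") and then adds: "If pregnancy falls outside of this time period, it would not need to be reported for the trial or monitored for adverse effects".

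Section 9.8 is the section on pregnancy. It says: "In the event of a trial participant or the partner of a trial participant becoming pregnant on the trial, the site must notify NCTU", along with the chief investigator and the sponsor's representative, within 24 hours of becoming aware. The site must also approach the participant or partner "to obtain consent to follow the pregnancy to completion". Section 9.8 mentions neither the last dose nor Table 2.

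Three other provisions bear on the point:

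- Section 8.4 sets the injection cycles at "day 0; week 12 +/- 7 days; week 24 +/- 7 days", and participants are followed to week 36.
- The Schedule of Events (7.4.10) has pregnancy tests at screening and at week 36 only. Footnote e reads "Pregnancy test required at 36 weeks for all participants of childbearing potential", with a later test 7 days on for those still taking TAU.
- Inclusion criterion 6 and section 6.3 require contraception or abstinence for the whole of trial involvement, not until 7 days after the last dose.

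**The concern.** The 7-day period was derived for monitoring serious adverse reactions, and the footnote carries it over to pregnancy. Read literally, it releases a site from reporting and monitoring a pregnancy in someone who is still on the trial, still required to use contraception, and still due a pregnancy test. Section 9.8 tells the same site to notify that pregnancy within 24 hours and to seek consent for follow-up.

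What is at stake is the consistency of a mandatory safety instruction. Sites may handle the same event differently. Where a site follows the footnote, the step that leads to the pregnancy outcome, namely consent to follow-up, may not be taken. No primary or secondary efficacy analysis is affected.

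**Working it through.** **1. The 7-day figure reproduces.** Five half-lives in hours, divided by 24 and rounded up to whole weeks:

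| Drug | Half-life (h) | 5 × half-life (h) | Days | Rounded up |
|---|---|---|---|---|
| Amitriptyline | 25 | 125 (table prints 155) | 5.2 (6.5 from 155) | 7 |
| Gabapentin | 7 | 35 | 1.5 | 7 |
| Lidocaine | 1.68 | 8.4 | 0.4 | 7 |
| Botox | 10 | 50 | 2.1 | 7 |

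The amitriptyline clearance figure does not equal five times its half-life, but the rounded result is 7 days either way.

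**2. Where the footnote's period ends.** End of period = week of last dose + 1. On-trial weeks outside it = 36 − (week of last dose + 1), not below zero, with week 36 taken at its nominal date.

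| Last dose | Period ends | Weeks outside, to week 36 | Share of 36 |
|---|---|---|---|
| Injection, week 24 | week 25 | 11 | 31% |
| Injection, week 23 (−7 days) | week 24 | 12 | 33% |
| Injection, week 25 (+7 days) | week 26 | 10 | 28% |
| Injection, stopped after week 12 | week 13 | 23 | 64% |
| Injection, stopped after day 0 | week 1 | 35 | 97% |
| TAU to week 36 | week 37 | 0 | 0% |
| TAU to week 35 | week 36 | 0 | 0% |
| TAU, last dose week 12 | week 13 | 23 | 64% |
| TAU, last dose week 8 | week 9 | 27 | 75% |

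The early-stopping rows are cases the protocol allows. Section 7.6 lets participants in any arm stop treatment and stay on the trial. Section 8.4 gives a minimum oral course of 8–12 weeks. Footnote g of the Schedule of Events limits the week-37 call to those still on TAU at week 36 or who stopped after week 35, so it foresees earlier stopping.

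**3. The two rules applied to one case.** Take an injection participant treated on schedule who tests positive at week 36.

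- Under section 9.8 she became pregnant on the trial, so notification is due within 24 hours and consent to follow-up must be sought.
- Under the footnote, if the pregnancy is dated by detection, it falls 11 weeks after the period closed. It need not be reported or monitored.
- If it is dated by conception, the answer under the footnote depends on whether conception was before or after week 25. The footnote does not say which date counts.

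If section 9.8 governs, the uncovered time is 0 weeks in every arm. If the footnote governs, it is the figure in step 2.

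**The case against.** The best case on the other side has four parts.

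*Section 9.8 still binds.* It is the dedicated section and its duty is mandatory. A reader might infer that pregnancies in weeks 25–36 go unreported. The documents do not support that: loss occurs only if a site follows the table footnote over section 9.8. This stands. The defect is two instructions that conflict, not a certain gap.

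*The rule is the same in all arms.* A reader might also infer that the injection arms lose these pregnancies while TAU does not. The footnote applies 7 days from last dose to all four drugs, and a TAU participant who stops at week 8 or 12 has more time outside the period than an injection participant on schedule. This stands too. Under the planned schedule the conflict reaches every injection participant and spares TAU taken to about week 35, but that comes from treatment length, not from separate rules by arm.

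*Little depends on it.* Pregnancy is neither a listed outcome nor a pre-specified adverse event. Section 9.8 says it is not in itself serious, and a congenital anomaly remains a reportable serious event. The weeks counted above are calendar time, not risk: the protocol gives no pregnancy rate and requires contraception throughout. This limits the weight of the point. However, a pregnancy beginning after week 25 would reach term after week 36, so its outcome is learned mainly through the follow-up consent that the footnote makes unnecessary.

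*The footnote may be meant only for the time after participation ends.* That is a reasonable guess at the intent. The text, however, counts from the last trial dose, and for injections that is about 12 weeks before participation ends.

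The week-36 test is a testing requirement, not a reporting rule. It is in tension with the footnote and does not contradict it outright.

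**Conclusion.** The conflict between the Table 2 footnote and section 9.8 is real and can be read directly from the text. For injection participants treated on schedule it covers about 11 of 36 weeks (31%; 10 to 12 weeks with the ±7-day window on the last injection), including the week-36 test. It also covers anyone in any arm who stops treatment early and stays on the trial, for longer the earlier they stop. TAU taken to about week 35 or later is not touched. These figures assume the planned injection schedule, week 36 at its nominal date, and a literal reading of the footnote.

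The documents do not support the stronger conclusions that such pregnancies will go unreported or that the protocol sets different reporting rules by arm. The point should be corrected because it concerns a mandatory safety instruction and costs almost nothing to settle. It does not bear on the co-primary analysis.

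**What to change.** Reconcile the Table 2 footnote with section 9.8 and with the week-36 pregnancy test, so that one unambiguous pregnancy-reporting rule applies and each place refers to it. The rule should say whether the date of conception or the date of detection decides if a pregnancy is inside the window. Which window is right is for the sponsor to decide. The cost is about one sentence in an amendment and a note to sites, with at most a few more pregnancy forms depending on the rule chosen.

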9.3. Pre-specified AEs

As part of the trial, a number of adverse events of interest relating to Botox and Amitriptyline and Gabapentin will be collected as part of routine data collection. The events below are the pre-specified adverse events of interest and will therefore be collected:

- New onset headache
- Facial weakness following Botox (see section 7.4.5 for assessment/recording details).
- Other adverse effects listed within the Liverpool adverse events profile.

All adverse events that are considered as possibly related to any of the trial IMPs must be reported for the trial on the Adverse Event CRF.

9.4. Protocol Specific Reporting Exclusions

The following condition will not need to be reported on an SAE form, but should be recorded in the database on the Adverse Event CRF page:

 Pre-planned hospitalisations (e.g. elective surgery) or scheduled treatment for pre-existing conditions that are not associated with clinical deterioration.

Worsening of pre-existing persistent pain conditions affecting the head and face are not reportable as AEs for the purpose of the trial, because of the natural chronological fluctuation of the pain intensity of all persistent head and face pain conditions (9.3). However, any event which is considered worse than usual and considered as possibly related to the trial IMP, must be reported as an AE / SAE and reported on an SAE form if appropriate.

ARs detailed in the RSI for the four trial IMPs (detailed in section 8.1) are not reportable as SUSARs

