9. PHARMACOVIGILANCE

9.1. Definitions

Term	Definition				
Adverse Event (AE)	Any untoward medical occurrence in a participant to whom a medicinal product has been administered, including occurrences which are not necessarily caused by or related to that product.				
Adverse Reaction (AR)	An untoward or unintended response in a participant to an investigational medicinal product which is related to any dose administered to that participant.				
	The phrase "response to an investigational medicinal product" means that a causal relationship between a trial medication and an AE is at least a reasonable possibility i.e. the relationship cannot be ruled out.				
	All cases judged by either the reporting medically qualified professional or the Sponsor as having a reasonable suspected causal relationship to the trial medication qualify as adverse reactions				
Reference Safety Information (RSI)	The RSI is a list of medical terms detailing the ARs that are expected for an IMP and must be referred to when assessing a SAR for expectedness.				
Serious Adverse Event (SAE)	 A serious adverse event is any untoward medical occurrence that: Results in death Is life-threatening* Requires inpatient hospitalisation or prolongation of existing hospitalisation. Results in persistent or significant disability/incapacity Consists of a congenital anomaly or birth defect Other important medical events that jeopardise the participant or require intervention to prevent one of the above consequences. * - life-threatening refers to an event in which the participant was at immediate risk of death at the time of the event; it does not refer to an event which hypothetically might have caused death if it were more severe. 				
Serious Adverse Reaction (SAR)	An adverse event that is both serious and, in the opinion of the reporting Investigator, believed with reasonable probability to be due to one of the trial treatments, based upon the information provided.				
Suspected Unexpected Serious Adverse Reaction (SUSAR)	A serious adverse reaction, the nature and severity of which is not consistent with the approved Reference Safety Information.				

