9.1.3. Assessment of causality of AEs

The relationship between the use of IMP and the occurrence of each AE must be assessed and categorised by the PI or delegated clinician using clinical judgement to determine the causal relationship. Other factors such as medical history of underlying diseases, concomitant therapy and any other relevant risk factors should be considered. The PI should also consult the current version of the Reference Safety Information as per section 8.1 and make a determination according to the definitions below:

Yes (related)	Event considered related to IMP
Probable	It is probable the event is related to IMP
Possible	It is possible the event is related to IMP
Unlikely	It is unlikely the event is related to IMP
No (unrelated)	Event considered unrelated to IMP
Unable to	After review of information available the PI/delegated clinician is unable to
determine	determine if event is related to IMP or not

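### Section 9.4 leaves out the severity test in the protocol's own SUSAR definition, and section 9.1 sets different causality thresholds for an AR and an SAR

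*Protocol*

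**What the plan says.** Section 9.1 of the protocol gives the definitions that decide what is expedited.

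- **SUSAR:** "A serious adverse reaction, the nature and severity of which is not consistent with the approved Reference Safety Information".
- **RSI:** "The RSI is a list of medical terms detailing the ARs that are expected for an IMP".
- **AR:** a causal relationship "is at least a reasonable possibility i.e. the relationship cannot be ruled out". Either of two parties may make the assessment: "All cases judged by either the reporting medically qualified professional or the Sponsor as having a reasonable suspected causal relationship to the trial medication".
- **SAR:** an event that is serious and, "in the opinion of the reporting Investigator, believed with reasonable probability to be due to one of the trial treatments".

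Section 9.1.3 grades causality in six categories: Yes, Probable, Possible, Unlikely, No, and Unable to determine. Possible is described as "It is possible the event is related to IMP". The section does not say which categories make a serious event an SAR.

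Section 9.4, which lists reporting exclusions, states: "ARs detailed in the RSI for the four trial IMPs (detailed in section 8.1) are not reportable as SUSARs".

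Section 9.2 requires an expectedness assessment by the chief investigator (CI) for each SAR. Section 9.5 requires all SUSARs to go to the MHRA and REC. The limit is 7 calendar days if fatal or life-threatening; otherwise 9.5 sets 15 calendar days for the MHRA. Site PIs are also informed.

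**The concern.** Sections 9.1 and 9.4 give the assessor two rules for the same decision. The first tests nature and severity. The second asks only whether the reaction is detailed in the RSI. Because 9.4 is headed as a set of exclusions, it reads naturally as an exception to the general duty in 9.5, and someone applying it literally would not come back to severity.

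One step earlier, the entry to the expectedness assessment is not clearly defined. An AR and an SAR differ in 9.1 by more than seriousness: the required strength of causality changes, and so does the person whose opinion counts.

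At stake is whether a qualifying reaction reaches the MHRA, the REC and the other sites within the time limits.

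**Working it through.** No figure in the plan bears on this point, so the check compares the rules case by case.

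**Step 1. Severity and choice of list (9.1 against 9.4).** Take a serious reaction accepted as related to the product received. The 9.1 column uses the RSI of that product.

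| Case | Under 9.1 | Under 9.4 as worded |
|---|---|---|
| A. Listed for the product received, severity consistent | Not a SUSAR | Excluded: agrees |
| B. Listed for the product received, more severe than listed | SUSAR | Excluded: conflicts |
| C. Not listed for the product received, listed for another trial product | SUSAR | Depends on the reading |
| D. Not listed for any trial product | SUSAR | Not excluded: agrees |

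Case B is a direct conflict. It rests on reading 9.1 so that inconsistency in either nature or severity is enough. If both had to be inconsistent, a listed reaction could never be a SUSAR, and the word severity would do no work in the definition. Severity is graded under 9.1.1 and recorded for every AE under 9.2, so the information is available; 9.4 simply does not use it.

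Case C turns on whether 9.4 means each product's own list or the four lists together.

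- For the product's own list: 9.1 defines the RSI for a single IMP, and 8.1 links the expectedness check to the IMP thought to be causal.
- For a pooled list: 9.4 names all four IMPs without linking each to its list, and 9.5 speaks of one RSI for the trial, contained in four SmPCs, without saying that the list must be that of the product received.

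**Step 2. Causality (AR against SAR).** Take a serious event and apply the two definitions to each category in 9.1.3.

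| Category | Meets AR wording? | Meets SAR wording? |
|---|---|---|
| Yes | Yes | Yes |
| Probable | Yes | Yes |
| Possible | Yes | Not on its face |
| Unable to determine | Arguably, since not ruled out | Not on its face |
| Unlikely | Unclear | No |
| No | No | No |

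The person whose opinion counts differs too. The Sponsor's view alone can make an event an AR. Under 9.6 the CI reviews causality of SAEs on the Sponsor's behalf where the CI did not make the original assessment. The SAR definition looks only to the reporting Investigator, so it gives an upgrade on that review no stated effect.

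**Step 3. What follows for expectedness.** Sections 9.2 and 9.5 attach the expectedness step to SARs. There are two ways to read the SUSAR definition:

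1. If the defined term SAR governs, a serious event rated only Possible is not an SAR and so is not a SUSAR. The stricter wording narrows the definition.
2. If it means any AR that is serious, the same event can be a SUSAR, but no text clearly triggers its expectedness assessment.

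The protocol does not say which is meant.

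**The case against.** The strongest reply is that other sections already do the work. All SAEs go to the trials unit within 24 hours whatever their causality (9.2). SARs and suspected SARs are passed automatically to the Sponsor and the CI (9.5). The CI reviews SAE causality (9.6) and assesses expectedness for each SAR (9.2), and the trials unit must see that this is done (9.5). Section 9.5 requires every SUSAR to be reported, with no exception stated there. On this view 9.4 is a shorthand that omits a qualifier found in the governing definition.

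Much of this stands, and it rules out three stronger readings that a reader might infer:

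- *That true SUSARs would certainly not be expedited.* The documents show two sections in conflict, and do not say which prevails.
- *That 9.4 definitely pools the four lists.* The wording in 8.1 and 9.1 points to the product concerned, and 9.5 sets out a separate SmPC for each product and asks for the name of the IMP in the minimum report. Pooling is one possible reading.
- *That the causality mismatch excludes events meeting the SUSAR definition, or that Unable to determine has no route to assessment.* If the SAR wording governs, such events never meet the definition; and suspected SARs and CI review give a possible route, though an unclear one.

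What the reply does not remove is the missing severity condition in a stated exclusion, or the two different causality tests. The safeguards bring the event to the assessor's desk; they do not tell the assessor which rule to apply.

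**Conclusion.** The point holds as an inconsistency in the safety-reporting rules. The severity conflict between 9.1 and 9.4 is plain on the wording, given that inconsistency in either nature or severity is enough for a SUSAR. Which RSI applies is left open. The AR and SAR definitions differ in both threshold and judge, and the causality scale is not mapped to either.

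In rule terms, one of the four cases in the first comparison is in conflict and one is ambiguous. Of the six causality categories, Possible is within the AR definition and below the SAR wording, and Unable to determine is unresolved. No frequency can be attached, because the SmPC lists are not reproduced. The exposure is misclassification, with a missed 7- or 15-day report and missed notice to sites. No event is lost, and no endpoint, sample size or analysis is affected. The correction should be made because a stated exclusion, followed literally, gives the wrong answer.

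**What to change.** Three changes of wording:

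1. **Section 9.4:** exclude from SUSAR reporting only SARs that are consistent, in both nature and severity, with the RSI of the IMP or IMPs the participant received. Align the RSI sentence in 9.5 with this.
2. **Section 9.1:** define an SAR as an AR that is also serious, with the same causality threshold and the same judges (the Investigator, or the Sponsor or the CI on its behalf).
3. **Section 9.1.3:** state which categories count as related for SAR and SUSAR purposes, consistent with that threshold. The AR wording takes in Possible; Unable to determine needs an explicit ruling.

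The SAE form should follow. The cost is a short amendment, a few more expectedness assessments, and possibly a few more expedited reports. Treatment, endpoints and analysis are untouched.
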